4.0 Study Intervention(s)/Investigational Agent(s)

- 4.1 Description:
 - We will use transcranial direct current stimulation (tDCS) to stimulate the dorsolateral prefrontal cortex (DLPFC).
 - tDCS is a non-invasive brain stimulation technique that can modulate brain connectivity.
 - tDCS involves applying a weak electrical current (1 to 2mA) to the scalp via anodal and cathodal electrodes, causing either increases or decreases in cortical excitability, respectively.
 - Research has shown in both healthy subjects and patients (e.g. Alzheimer's disease, Parkinson's disease, stroke, and depression) that tDCS has the potential to modulate synaptic strengthening and

neurotransmitter-dependent plasticity underlying changes in behavior and learning (Lang et al., 2005).

- 4.2 Drug/Device Handling:
 - tDCS will be applied with a StarStim Enobio system (Neuroelectrics, Barcelona, Spain) using a bipolar stimulation montage.
 - This device has been approved for use in research without an investigational device exemption due to meeting criteria for non-significant risk (NSR).
 - In addition, the device has built in safety mechanisms which allow for the immediate cessation of stimulation should the subject become uncomfortable or if the impedance of the stimulation electrodes is too high.
 - The current will be administered via two saline soaked sponge electrode sponges during each intervention session, using a current strength of 1.0 to 2.0 mA.
 - These administration procedures are in line with other protocols that have outlined the safe use of tDCS in pediatric populations (Antal et al., 2017).
 - The tDCS cap and stimulation electrodes/sponges will be washed and disinfected after each intervention session and stored under lock and key in [name].
- 4.3 IND/IDE: N/A

5.0 Procedures Involved

- 5.1 Study Design:
 - The study will be a randomized, double-blind, placebo (sham) controlled trial.
 - Eligible participants will be randomized to treatment or placebo in a 1:1 allocation ratio (n=20 active tDCS, n=20 sham).
 - Randomization will be from a computer procedure for randomization and tracking.
 - All members of the team will be blinded to assignment.
 - A block randomization procedure with variable block sizes will be used to maximize unpredictability of assignment.
- 5.2 Study Procedures:
 - Intervention (active tDCS vs. sham): There will be a total of 6 visits for the study an initial baseline and intervention visit; four

additional intervention visits and one follow-up visit (within one week of the last intervention session)

- Visit 1: Baseline session; three hour visit.
 - a. Obtain consent; conduct safety screen for MRI (15 min)
 - b. Baseline MRI scan (45 min)
 - c. Baseline cognitive testing (60 min)
 - d. First tDCS intervention session (60 min)
 - i. 14 minutes set-up
 - ii. 46 minutes of cognitive training interleaved with two 13 minute blocks of active or sham tDCS (26 minutes total active/sham tDCS)
- Visits 2-5: tDCS intervention sessions; one hour visits.
 - a. 14 minutes set-up
 - b. 46 minutes of cognitive training interleaved with two 13 minute blocks of active or sham tDCS (26 minutes total active/sham tDCS)
- Visit 6: Follow-up; two hour visit. Within one week of the last intervention session
 - a. Obtain consent/screen for MRI (15 min)
 - b. Repeat MRI scan (45 min)
 - c. Repeat cognitive testing (60 min)
- Cognitive Training Description (Brain HQ):
 - 46 total minutes of cognitive training using the BrainHQ software (Posit Science, San Francisco, CA) will be completed by each subject in each intervention session.
 - The BrainHQ software includes a number of brain training games which focus on various aspects of attention, reaction time, memory and executive function.
 - Positive findings using the BrainHQ program have been reported in children with ADHD (Mishra, Merzenich, & Sagar, 2013) as well as adults with traumatic brain injury (Lebowitz, Dams O'Connor, & Cantor, 2012).
 - The BrainHQ program allows for real-time monitoring of subject performance and adjusts the difficulty level of individual tasks accordingly.

- Additionally, it allows for quantitative tracking of subject performance over time both within and across intervention sessions.
- tDCS Description:
 - Two 13 minute blocks of active or sham 1.0 to 2.0 mA tDCS will be applied in parallel with cognitive training in each intervention session.
 - A 20 minute block of cognitive training without active or sham tDCS will separate the two 13 minute active or sham tDCS blocks with cognitive training.
 - The sham condition will emulate the sensation of tDCS on the scalp at the beginning and end of each 13 minute stimulation block in order to blind the subject to the intervention type, however, current will not be applied for the remainder of the 13 minute blocks.
 - tDCS will be applied with a StarStim Enobio 8 system (Neuroelectrics, Barcelona, Spain) using a bipolar stimulation montage (anode over the left DLPFC/F3 and cathode over the right orbitofrontal cortex/FP2).
 - The StarStim device allows for double-blinded administration of tDCS/sham stimulation during each session.
- Neuroimaging:
 - Pre- and post-intervention fMRI will be collected to examine resting state connectivity changes and reversal learning task changes.
 - a. Subjects will be scanned at the Center for Magnetic Resonance Research on a Siemens Prisma scanner using Human Connectome Project accelerated imaging (Glasser et al., 2016).
 - b. A high resolution structural scan and a select period of resting-state fMRI (eyes open and eyes closed) will be collected.
 - c. fMRI during a reversal learning task will also be collected. Our group has previously used this task to assess brain function related to cognitive flexibility and executive function.

- Analysis will be done using already published functional connectivity approaches (Haut, [name], & MacDonald, 2010; [name] et al., 2016).
- Assessments: Note that all instruments are to be administered for research purposes (not for clinical diagnostic or treatment purposes). Standard precautions will be implemented to reduce potential frustration and fatigue (frequent breaks, positive feedback about performance, etc.)
 - The following assessments will be administered to the child using the NIH toolbox using an iPad:
 - a. NIH Toolbox Flanker Inhibitory Control and Attention Test measures both a participant's attention and inhibitory control. (Heaton et al., 2014)
 - b. NIH Toolbox Dimensional Card Sort Test (DCCS) is an assessment to measure of cognitive flexibility.
 - c. NIH Toolbox Picture Sequence Memory Test (PSMT) is a measure for use in the assessment of episodic memory.
 - d. NIH Toolbox Oral Symbol Digit Test (OSDT) is a measure of processing speed. (Denboer, Nicholls, Corte, & Chestnut, 2014).
 - The following additional assessments will be administered to the child:
 - a. Subtests from the Delis-Kaplan Executive Functioning System (DKEFS): a standardized battery of executive functioning.
 - The following questionnaires will be administered to the parent:
 - a. Parent and Child Questionnaire
 - b. Behavior Assessment System for Children 3nd
 Edition (BASC-3): a standardized parent-report questionnaire of typical and atypical child behavior.
 - c. Delis Rating of Executive Functioning (D-REF): a standardized parent-report questionnaire of child planning, organization, attention, inhibition, and emotional control.
 - The tDCS Report of Symptoms questionnaire will be administered to the child before and after each tDCS/sham intervention:

- a. Assessment tool to monitor for common, specific side effects noted across many existing tDCS studies, including but not limited to itching, prickling, burning sensation, nausea, fatigue and headache.
- b. Approximately 3-5 minutes to administer and is typically performed twice during each intervention session (once before and once after the session).
- c. Furthermore, participants will be continuously monitored by a member of the study staff throughout each intervention session to ensure comfort and safety.
- d. In addition, at the end of each intervention visit, the subject will be asked if they think they received the active or sham condition.
- All forms are attached to this submission

5.3 Follow-Up: Participants will be contacted by phone 30 days after the last intervention session. The tDCS Report of Symptoms questionnaire will be administered.

- 5.4 Individually Identifiable Health Information: See attached HIPCO Ancillary Review Form and HIPAA Authorization form
- 5.5 Use of radiation: NA neither MRI nor tDCS uses ionizing radiation
- 5.6 Use of Center for Magnetic Resonance Research: This study uses the CMRR and follows all CMRR protocols and procedures.

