1.0 Objectives

- 1.1 Purpose:
 - Aim 1: Characterize the feasibility and tolerability of combined cognitive remediation and tDCS in children ages 10-16 with FASD.
 - Hypothesis 1: Children with FASD will tolerate the procedures and remain in the study with less than 20% dropout over the course of cognitive remediation and tDCS
 - Aim 2: Evaluate the potential additive benefits of tDCS to the base cognitive remediation program.
 - Hypothesis 2: Cognitive remediation with active tDCS vs. sham tDCS will result in greater gains over the courses of treatment.
 - Aim 3: Examine the brain circuitry changes following the intervention.
 - Resting and task fMRI will demonstrate greater change with active compared with sham tDCS.

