11.0 Local Number of Participants

11.1 Local Number of Participants to be Consented: Up to 60 participants will be consented in this study, with the goal of having 40 participants enroll and complete the full study.

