16.0 Data Management

- *16.1* Data Analysis Plan: Data analyses will include traditional statistical analyses for group differences in neurocognitive and brain measures with control for confounding variables, multiple comparisons, etc.
- 16.2 Power Analysis: We propose to compare changes in cognition and in brain circuitry between the two intervention arms. With an n=20, alpha 0.05, power of 0.8, we have power to detect an effect size of 0.9.
- *16.3* Data Integrity: Neuroimaging data will be subjected to standard quality control measures (both automated and manual) including measuring and controlling for artefacts. Neurocognitive data will be checked for quality by more than one research staff member.

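### Does it matter that the protocol does not say whether 20 per arm means children randomised or children completing?

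*Combined protocol and SAP*

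**What the plan says.** Four places give a sample size, each in its own terms.

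- The Study Summary gives 40 participants, without saying whether they are randomised or completing.
- Section 5.1 (Study Design): "Eligible participants will be randomized to treatment or placebo in a 1:1 allocation ratio (n=20 active tDCS, n=20 sham".
- Section 11.1: "Up to 60 participants will be consented in this study, with the goal of having 40 participants enroll and complete the full study".
- Section 16.2 (Power Analysis) defines its comparison, "We propose to compare changes in cognition and in brain circuitry between the two intervention arms", and then states: "With an n=20, alpha 0.05, power of 0.8, we have power to detect an effect size of 0.9".

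Three other parts bear on the point. Hypothesis 1 in section 1.1 expects that children will "remain in the study with less than 20% dropout over the course of cognitive remediation and tDCS". Section 13.2 ends follow-up at withdrawal, and 13.3 permits use of data collected before it. In section 5.2 the second round of measurements is at Visit 6: "Repeat MRI scan (45 min" and "Repeat cognitive testing (60 min".

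**The concern.** Read literally, 5.1 fixes the number randomised at 40, and 11.1 wants 40 to finish. Both are met only if nobody drops out, and Hypothesis 1 shows that the investigators expect some dropout. No section gives an expected loss or a replacement rule, or says whether the 20 consents beyond 40 (60 − 40) cover losses before or after randomisation.

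Section 16.2 does not settle it, because its n=20 is unlabelled. If it means 20 randomised per arm, the printed 0.9 makes no allowance for loss. Taking changes in cognition and brain circuitry to be the tests and scans repeated at Visit 6 (16.2 does not name its measures), each withdrawal before that visit removes a child from the powered comparison. The stake would be a power statement that is somewhat too favourable, together with an unclear denominator for the 20% dropout criterion.

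**Working it through.** **Inputs.** 20 per arm, 1:1 (5.1); n=20, alpha 0.05, power 0.8, standardised effect 0.9 (16.2); goal of 40 completing and cap of 60 consents (11.1). Section 16.2 gives neither sidedness nor method. Two-sided is assumed here.

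**Step 1: reproduce 0.9.** By the normal approximation the detectable effect is

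d = (z₀.₉₇₅ + z₀.₈₀) × √(1/n₁ + 1/n₂) = (1.960 + 0.842) × √(1/20 + 1/20) = 2.802 × 0.316 = 0.886.

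The non-central t gives 0.909, with power 79.2% at an effect of 0.9. Both round to the printed 0.9. Taking n=20 as the total (10 per arm) gives 1.32 by t, and a one-sided test at 20 per arm gives 0.80. The figure therefore means 20 evaluable per arm, two-sided, and its arithmetic is right.

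**Step 2: what if exactly 40 are randomised and some are lost before Visit 6?** The documents give no expected loss, so these rows are assumptions.

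| Evaluable | Lost of 40 | Power at 0.9 (t) | Detectable effect, t | Detectable effect, normal |
|---|---|---|---|---|
| 20+20 | 0 | 79.2% | 0.909 | 0.886 |
| 19+19 | 2 (5%) | 77.0% | 0.934 | 0.909 |
| 18+18 | 4 (10%) | 74.6% | 0.961 | 0.934 |
| 16+16 | 8 (20%) | 69.3% | 1.024 | 0.991 |

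At 18+18 the result still rounds to 0.9 by the normal approximation, but to 1.0 by the t. Since 16.2 names no method, a one-decimal figure cannot be called wrong at that level of loss.

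**Step 3: is there a reading under which the sections agree?** Take 20 per arm as the evaluable target. The summary's 40, the 40 completing in 11.1 and the n=20 in 16.2 then coincide, and the consents beyond 40 are the allowance. The order of events supports this. Telephone screening comes before consent (9.3, 21.2), which should remove many ineligible children before the 60 are counted. Consent, baseline scan, baseline testing and the first stimulation session all fall in Visit 1 (5.2), so there is little room for loss between consent and first intervention. The spare consents plausibly serve later dropout. At an assumed 20% loss, 40/(1 − 0.20) = 50 would have to be randomised, which is below 60.

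**Step 4: would exact balance be needed?** No. If 40 complete as 22+18, power at 0.9 is 78.8%, against 79.2% at 20+20. Randomisation could continue without arm-specific replacement, so the blinding in 5.1 ("All members of the team will be blinded to assignment") is not disturbed.

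**Step 5: the dropout denominator.** A pass/fail reversal can be constructed: 8/40 = 20.0% misses the criterion of under 20%, while 8/48 = 16.7% meets it. It requires dividing by a planned 40 when 48 were randomised. If 40 are randomised, both denominators are 40. If 48 are randomised, the natural denominator is 48.

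**The case for a change.** The strongest opposing case is that 5.1 does attach 20+20 to randomisation, and the reading in Step 3 is an inference that no sentence confirms. A coordinator with 40 randomised and three withdrawn could not tell from the protocol whether to stop or continue. If the team stops at 40, the only power statement in the document is optimistic for the Visit 6 changes, and feasibility, the stated primary objective, has a numerical criterion without a written denominator.

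The missing definition stands, and so does the direction of the effect: with exactly 40 randomised, any loss lowers power. What does not follow is a contradiction. Section 11.1 states a goal, and falling short of a goal breaches nothing in 5.1. Stopping at 40 or continuing within the 60 consents both leave an interpretable trial. The primary endpoints in 3.1 are the BrainHQ learning curves, which build up session by session and can use data from children who withdraw (13.3), so the loss falls mainly on the secondary pre/post measures.

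**Conclusion.** This is a gap in definition that analysts fill sensibly, and no change to the plan is needed. They would report how many children were randomised, how many reached Visit 6, and dropout as a share of those randomised. The only printed power figure reproduces, and 20 evaluable per arm is consistent with the summary, 11.1 and 16.2, with up to 60 consents as the margin.

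If exactly 40 are randomised, the cost is modest. With two to four lost evenly, the detectable effect moves from about 0.9 to 0.93–0.96 by the t, or 0.91–0.93 by the normal approximation. Even an assumed loss of eight brings it only to about 1.0. These figures assume a two-sided two-sample comparison and illustrative loss rates. The limit in Hypothesis 1 covers the training period, so it neither predicts nor bounds loss at Visit 6. In a pilot, a shift of this size does not alter the design or the way its results would be read.

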8.0 Study Duration

- 8.1 Describe:
 - Participants will complete the 6 visits described above, typically within a span of 8 weeks maximum.
 - All study participants will be enrolled within the two year timeframe of the study.
 - Data analysis is expected to continue for 1-2 years post study conclusion.

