12.0 Local Recruitment Methods

- 12.1 Recruitment Process: Families of potential participants will be contacted by research staff or will initiate contact themselves. Visitors to the clinics described below may see flyers and brochures describing the study at the time of their clinic appointment although they will not be recruited directly by their clinician. Mailings will also be sent to families of children with FASD via lists provided by the Minnesota Organization on Fetal Alcohol Syndrome (MOFAS). MOFAS has close working relationships with [name], [name], [name], [name] and both clinics. All recruitment materials will be submitted for IRB approval upon development, before use in the study. Telephone scripts will be utilized.
- 12.2 Source of Participants: Participants will be recruited from two University of Minnesota Medical Center Clinics in which co-investigators see patients: The Fetal Alcohol Spectrum Disorders clinic ([name], Ph.D., [name], Ph.D) and the International Adoption Clinic (directed by [name], M.D.).
- 12.3 Identification of Potential Participants: Potential participants will selfidentify in some cases based on advertisements. In other cases, participants will be recruited based on having been seen for an evaluation for FASD. Participants will not be recruited by a clinician (to avoid potential coercion and/or confusion about clinical care vs. research. Instead, research staff will contact families and will conduct telephone screens to determine eligibility. Access to contact information for potential participants will be obtained from the clinicians who are co-investigators on the study ([name], [name], and [name]). Patients who "opted out" of allowing their clinical data to be utilized for research via the standard UMMC / Fairview clinical consent form will not be recruited.
- 12.4 Recruitment Materials: See attached recruitment materials in ETHOS.
- 12.5 Payment: Participant families will receive payment (check or pre-paid card) for participation. Because the participants are children, the payment will be provided to the parent on behalf of the child. Payment will be made at the completion of the study (final visit) or at the time of a participant dropping out of the study. Payment will be based on procedures attempted and/or completed as follows:
 - \$50 for the neuropsychological testing and parent rating forms
 - \$50 for each MRI scan (\$100 total)
 - \$25 for each tDCS session (\$125 total)

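### After the last session, no symptom report is scheduled until a phone call 30 days later, although the child attends Visit 6 within a week; the stated duration also leaves out that call

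*Combined protocol and SAP*

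**What the plan says.** **Symptom reports.** Section 5.2 (Assessments) ties the tDCS Report of Symptoms to the intervention sessions. It takes about 3-5 minutes and is "typically performed twice during each intervention session (once before and once after the session"). Section 5.3 adds one later contact: "Participants will be contacted by phone 30 days after the last intervention session". The instrument is the same: "The tDCS Report of Symptoms questionnaire will be administered". Section 5.3 does not say who answers at the call or what period the answers cover. The forms are described as attached to the submission and are not part of the text.

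**Visit 6.** Section 5.2 describes it as "Visit 6: Follow-up; two hour visit. Within one week of the last intervention session". It has three items: "Obtain consent/screen for MRI (15 min"), "Repeat MRI scan (45 min") and 60 minutes of repeat cognitive testing. None is a symptom report.

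**Duration.** The Study Summary gives 4-8 weeks for an individual participant. Section 8.1 says: "Participants will complete the 6 visits described above, typically within a span of 8 weeks maximum". Neither mentions the call. Section 12.5 says: "Payment will be made at the completion of the study (final visit"), or on dropping out.

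**General safety text.** Section 14.1 says adverse events go to the IRB, and section 18.0 makes the principal investigator responsible for safety monitoring. Neither schedules a symptom inquiry at any visit.

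**The concern.** Aim 1 is about feasibility and tolerability, and this questionnaire is the only scheduled instrument directed at side effects of stimulation. After sessions 1-4, the child is asked again before the next session. After session 5 the next scheduled question comes a month later, although staff see the child in person in the meantime.

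What is at stake is how much a quiet 30-day call can show. Section 14.1 names sores at the electrode site and headaches that temporarily affect comfort or functioning. Something that began two days after session 5 and cleared within the week would be recorded only if the family volunteered it or remembered it at day 30. Section 2.1 lists attention and working memory among the common problems in FASD, so month-long recall is a weak basis if the child is the one asked.

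The duration figures raise a smaller matter. Families are given a participation period, and staff plan around it. If it stops at Visit 6, the last safety contact lies outside the period described.

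**Working it through.** **1. Schedule of symptom reports**, from sections 5.2 and 5.3, with session 5 as time zero:

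| Contact | Timing | Symptom report scheduled? |
|---|---|---|
| Sessions 1-5 | before and after each | yes, 2 x 5 = 10 |
| Visit 6 | 0-7 days after session 5 | no |
| Phone call | 30 days after session 5 | yes, 1 |

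The first scheduled interval after treatment is 30 days. With a report at Visit 6 it would be at most 7 days, and the interval from Visit 6 to the call would be 30 - 7 = 23 to 30 - 0 = 30 days.

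**2. Exposure at that point.** Each session has two 13-minute blocks, so 2 x 13 = 26 minutes. The running total of assigned stimulation time after sessions 1-5 is 26, 52, 78, 104 and 130 minutes. Session 5 completes the cumulative exposure, but it is no longer than the others.

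**3. Room at Visit 6.** 15 + 45 + 60 = 120 minutes, which is the whole two-hour visit. Adding the form makes it 123-125 minutes.

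**4. Does the conclusion depend on the form's recall window?** The text does not give it, so both readings are set out:

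| If the form asks about | Day-30 call gives | Form at Visit 6, worded to cover the time since session 5, gives |
|---|---|---|
| symptoms now | the state at day 30 only | the first 0-7 days |
| the time since last asked | the whole interval, on 30-day recall | the first 0-7 days, on recall of at most 7 days |

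The added report supplies something new under either reading, provided its wording looks back to the last session.

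**5. Duration.** Count Visit 1 as day 0 and let D be the day of session 5. Then call day = D + 30, and Visit 6 falls between D and D + 7. The spacing of sessions is not stated, so the 4-8 week figure cannot be rebuilt from its parts. Its upper end equals the 8-week maximum that section 8.1 gives for the six visits alone.

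- Visits span 4 weeks (Visit 6 on day 28): D = 21 to 28, so the call is on day 51-58, or 51/7 = 7.3 to 58/7 = 8.3 weeks.
- Visits span 8 weeks (Visit 6 on day 56): D = 49 to 56, so the call is on day 79-86, or 79/7 = 11.3 to 86/7 = 12.3 weeks.
- The call falls within 8 weeks when D + 30 <= 56, that is, D <= 26.
- The call falls within 4 weeks when D + 30 <= 28, that is, D <= -2, which is impossible. Even if the five sessions were on consecutive days (an assumption), D = 4 and the call is on day 34, or 4.9 weeks.

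**The case against.** **The days after session 5 are not wholly uncovered.** A reader might infer that they go unmeasured. The documents do not support that. Session 5 has its own before and after reports, staff watch the child throughout, adverse events can be reported at any time, and the call may look back over the month. What is missing is a scheduled question in one interval. Nor would it be right to say that a fifth of session data is lost, since every session has both of its reports.

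**The recall window is unknown.** One might argue that the day-30 report must read near zero because the protocol expects effects to resolve on stopping. That holds only if the form asks about the present. On that reading, the before-session reports do not look back either, so sessions 1-4 have a similar gap. This stands, and it is why the point rests on the schedule and not on a prediction of what the call would show.

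**If effects resolve on stopping, the report straight after session 5 is the informative one.** This is largely right for the mild effects the protocol expects. It does not cover anything that begins or persists after the child leaves, which is the reason for having any later contact.

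**Hypothesis 1 is unaffected.** This is correct. Its criterion is dropout below 20% over the course of treatment. The link is to the broader tolerability aim.

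**The duration statements need not conflict with the call.** Section 8.1 limits its 8 weeks to the visits, and the call is not a visit. A reader might infer that the call always falls outside 4-8 weeks, but it does not if session 5 is on or before day 26. A reader might also take payment at the final visit to mean that participation ends there. Section 5.3 plainly schedules a later contact, so that inference fails. What remains is that the Study Summary's individual duration omits the call.

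**Conclusion.** The point holds as a missed opportunity. The plan has the child in the building within 7 days of completing 130 assigned minutes, has a 3-5 minute form in use, and does not schedule it. The first post-treatment symptom interval is 30 days and could be at most 7.

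This applies to all 40 planned participants, 20 per arm. The schedule is the same in both arms, so it does not in itself bias the active-sham comparison. It limits what can be said about the first week after treatment. The documents give no basis for estimating how many symptoms would be missed, and none is claimed.

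The 4-8 week duration needs restating. It cannot include the call at its lower end, and if the visits use the full 8 weeks, the call comes at about 11-12 weeks.

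The conclusion rests on two things: that the listed contents of Visit 6 are complete, and that no unseen form adds a symptom question there. If an attached form does so, only the duration point remains.

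**What to change.** - **Section 5.2, Visit 6:** add an item d, giving the existing tDCS Report of Symptoms to the child before the MRI and testing, worded to cover the time since the last session. Asking the parent as well is optional.
- **Section 5.3:** keep the 30-day call. State the period its questions cover and who answers.
- **Study Summary and section 8.1:** describe individual participation as six visits over 4-8 weeks plus a phone call 30 days after the last session, about 7-12 weeks in total when the visits take 4-8 weeks.

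The cost is about 3-5 minutes on a visit already booked for 120, and a small change of wording in the protocol and consent form. Asking the parent would add a little more time. No new visit or instrument is needed.
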